2.3.2. Secondary Outcomes

The secondary outcome is HIV Cascade Variables.

- Record/chart abstraction will be conducted for all patients in care at the site for
 - the 12 months prior to the start of implementation;
 - the 12 months during implementation; and
 - 6 months after the end of the implementation intervention.
- These data will include the date of diagnosis and care entry, antiretroviral adherence prescriptions, CD4 counts, viral load, and the CD4 and viral load testing dates.
- Retention in care variables will include: missed visits (using an absolute count or a minimum number of missed visits); Appointment adherence (proportion of scheduled visits that are kept); Persistence/constancy (a minimum standard of visits/time period, attending at least 1 visit every 90 days); and gaps in care (no more than 4 months without a visit). In addition, number of youth receiving HIV C&T services from the site as well as number of new diagnoses identified and linked to care will also be captured.

2.4. Key Updates

[To document any adjustments to the SAP as the manuscript progresses]

SAP Version	Changes Made	Rationale	Effective Date

3. STUDY METHODS

3.1. Study Design

The hybrid type-3 implementation-effectiveness trial used a Dynamic Wait-Listed Design (DWLD) to evaluate the impact of TMI and CoP on provider MI competency and HIV care cascade outcomes. Ten adolescent HIV sites in the United States were randomly assigned to one of five clusters, which determined the timing of the TMI implementation intervention. There

were three study phases, baseline, implementation, and sustainment, each of which included repeated measurements of provider MI competency. Across the 10 sites, there were 139 participating providers and cascade outcomes for [N] patients.

At the time of each randomization, the two sites were randomly selected as a cluster to enter the TMI implementation phase, with the other clusters remaining in the baseline phase. This continued until all blocks were randomized to the TMI implementation phase. After each cluster received one year of TMI implementation, a second randomization assigned the two sites in each cluster to the sustainment phase condition, either CoPs or CoPs plus internal facilitation monitoring and coaching. For each cluster, the duration of this phase was variable (e.g., 17 months for the first cluster, 6 months for the last cluster), with each ending at the end of study data collection (May 2020). MI competency was assessed on a quarterly basis across the baseline, implementation, and sustainment phases.

3.2. Randomization

With the DWLD, the 10 sites, in groups of two, were randomly assigned to one of five clusters. To allow sufficient time for scheduling and planning the initial workshop component, each wave of randomization occurred six months prior to the workshop month, which was three months prior to the first pre-intervention fidelity assessment. At each wave of randomization, two of the remaining (i.e., untrained) sites were randomly selected for the next wave of implementation. The specific randomization method involved several steps, each of which was implemented using SPSS software: (1) The full list of sites was entered, (2) each site had a dichotomous Intervention Status indicator (0 = No, 1 = Yes) to reflect whether it had been randomized to the implementation intervention. There were also fields to record the randomization date and initial workshop date. (3) For each wave of randomization, the data were sorted in ascending order by training status and site name. (4) A new random number variable was created for each wave. The assigned random value was obtained using the SPSS random number generator, set using the Mersenne Twister algorithm with a random starting point, and computed using the random uniform function with minimum and maximum values specified as 100000, 999999. (5) After a new random number was assigned to each site, the data were be resorted in ascending order by intervention status and the random number variable. (6) The first two sites (those with the lowest randomly assigned numbers) were selected for the next wave of training. This process was repeated for each subsequent wave of randomization. Drs. [name] and [name] were responsible for implementing the randomization procedure, and TMI study staff were responsible for communicating the randomization results to sites.

3.3. Sample Size and Power Calculation

The final sample size was 10 sites, and 151 providers. For the HIV care cascade outcomes, there were 1462 individuals.

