10.0 Subject Population*

The table below provides a breakdown of the current participant pool and participation in the beginning of cycle 8. Participants are affiliated with clinical sites within the ATN.

PROGRESS BY SITE		
Site 1		
17	Total Consented	
6	Discontinued TMI participation	
11	Active (current participants)	
0	Completed this cycle	
11	Not completed	
Site 2		
19	Total Consented	
6	Discontinued TMI participation	
13	Active (current participants)	
2	Completed this cycle	
11	Not completed	
Site 3		
18	Total Consented	
8	Discontinued TMI participation	
10	Active (current participants)	
0	Completed this cycle	
10	Not completed	
Site 6		
29	Total Consented	
9	Discontinued TMI participation	
20	Active (current participants)	
3	Completed this cycle	
17	Not completed	
Site 7		
18	Total Consented	
3	Discontinued TMI participation	
15	Active (current participants)	
1	Completed this cycle	
14	Not completed	
Site 8		
16	Total Consented	
4	Discontinued TMI participation	
12	Active (current participants)	
0	Completed this cycle	
12	Not completed	
Site 10		
11	Total Consented	
1	Discontinued TMI participation	
10	Active (current participants)	
0	Completed this cycle	
10	Not completed	
Site 11		
15	Total Consented	
4	Discontinued TMI participation	
11	Active (current participants)	
0	Completed this cycle	
11	Not completed	
Site 12		
24	Total Consented	
5	Discontinued TMI participation	
19	Active (current participants)	

PROTOCOL TITLE: TMI

0	Completed this cycle
0	Not completed
Site 13	
23	Total Consented
5	Discontinued TMI participation
18	Active (current participants)
2	Completed this cycle
16	Not completed
TOTAL	
190	Total Consented
51	Discontinued TMI Participation
139	Active (current participants)
8	Completed this cycle
112	Not completed this cycle

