3.3.1. Primary Objective

For Aim 1 (i.e., the effect of TMI on provider MI competence), estimation of power for mixed-effects regression models is complex because of the number of parameters involved, and in the present case, this is further complicated by the DWLD. Traditionally, and for conventional mixed-effects power analysis software, intervention condition is modeled at the highest level, and the intervention effect is the cross-level interaction between condition and a level-1 growth term. In the present case, because each provider has measurements in each of three research phases—that is, the intervention condition changes over time for each provider—the terms for testing the intervention effect are modeled at level-1 (i.e., time and phase terms). As such, a special method was required to estimate power, which was based on Hox (2018). There were three steps: (1) Compute the *actual* sample size of observations. For the primary outcome of provider MI competence, with 10 sites, an average of 18.9 providers each, and an average of 6.5 measurements per provider, there were 1,237 observations (i.e., non-independent, nested observations). (2) Penalize the sample of observations for nesting effects using a reorganization of the design effect formula (i.e., $neff = n / \{1+nclus - 1\} \rho$), the result of which is the *effective* sample size: the sample size of truly independent observations after adjusting the observed sample size for nesting effects that decrease statistical power. This step was performed twice, first to adjust for repeated measurements within providers and then to adjust for providers within sites. The supplied values for ρ were based on estimates from a fully unconditional, three-level mixed-effects regression model for the MI competence outcome. Note that the final models will not estimate a random effect for sites (due to the small number), and instead, they will control site effects using fixed effect indicators. For the purpose of power analysis, the site penalty was applied to provide a more conservative estimate. For the provider MI competence outcome, with a nesting effect of $\rho = .35$ for repeated measurements within providers, the sample of 1,237 non-independent observations provides the statistical power of 420 independent observations. The sample of 420 observations, with a nesting effect of $\rho = .09$ for providers in sites, provides statistical power equivalent to 90 truly independent observations. (3) Power was then estimated for a conventional, single-level regression model with the effective sample size of independent observations, which indicated that the effective sample of 90 independent observations was sufficient to detect a small-to-medium effect of $R^2 = .09$. Thus, power is sufficient to detect the effects of interest, though it is important to note that, due to the specific features of the design, this method did not directly account for the number of parameters in the model or the reliability of estimated slopes.

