5.1.5. Analysis Population

Intention-to-treat analyses will be performed, with each provider retained in the original site, cluster, and intervention phase corresponding to the measurement occasion.

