5.4.2. Secondary Objective (*as needed*)

5.4.3. Other Objectives (*as needed*)

5.5. Missing Data Procedures

There are two aspects of missing data procedures. The first relates to missing responses to individual items at a given measurement occasion, and the second relates to measurement occasions that are missed entirely by some participants. For TMI, the former is less of a concern, with low rates of observed missingness that can be remedied by standard scoring procedures (e.g., use of average scores rather than total scores). However, given the real-world implementation focus of TMI, there is substantial missingness of measurement occasions across providers. To address this, key considerations include the reasons for missingness, the amount of missingness, the nature of the missingness mechanism, and the resulting statistical remedies.

The primary outcome of MI competency was based on observer ratings across 12 items, and there were no missing item responses; thus, the primary missing data consideration pertains to missed measurement occasions. Across five blocks and ten sites, there were 189 providers. Of these providers, 99% had at least one MI competency measurement in the baseline phase (i.e., prior to the workshop), 75% had at least one measurement during the implementation phase, and 49% had at least one measurement during the sustainment phase. Given the decrease in completed assessments across the three phases, analyses will be performed to determine whether the likelihood of missingness was associated with baseline MI competency or other provider demographic characteristics. A pattern-mixture approach will also be used to determine whether the amount of change between baseline and implementation differed for providers who were missing sustainment data. Combined, the analyses will identify any potential evidence of a non-random missing data pattern that, if identified, can be controlled in subsequent analyses. Assuming there is no evidence of a non-random missingness mechanism, the analytic strategy will be to rely on maximum likelihood estimation, utilization of all available data, and estimation of individual slopes for each provider.

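### The SAP gives three unreconciled provider counts (139, 151, 189); only 189 fits its own calculations, and the analysis population has no stated size or membership rule

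*SAP*

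**What the plan says.** The SAP counts providers at the same ten sites in four places:

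- **SAP 3.1 (Study Design):** "Across the 10 sites, there were 139 participating providers and cascade outcomes for [N] patients".
- **SAP 3.3 (Sample Size and Power Calculation):** "The final sample size was 10 sites, and 151 providers".
- **SAP 3.3.1 (power for the primary objective):** "with 10 sites, an average of 18.9 providers each, and an average of 6.5 measurements per provider, there were 1,237 observations".
- **SAP 5.5 (Missing Data Procedures):** "Across five blocks and ten sites, there were 189 providers". Of these, 99% had a baseline measurement, 75% an implementation measurement and 49% a sustainment measurement.

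SAP 5.1.5 (Analysis Population) declares intention-to-treat, with "each provider retained in the original site, cluster, and intervention phase corresponding to the measurement occasion". It attaches no number.

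The site table in Protocol 10.0, repeated in 26.0, describes the beginning of cycle 8. It totals 190 consented, "51 Discontinued TMI Participation" and 139 active. Protocol 1.0 labels 139 as the current N. Protocol 9.0 and 13.0 say that enrolment is closed. Protocol 14.0 keeps the data of people who leave unless they ask for removal.

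**The concern.** The headline sample size in 3.3 disagrees with the power calculation directly beneath it, and both disagree with the design section. Because 5.1.5 gives no count and no membership rule, a reader cannot tell from that section which number the primary analysis should contain.

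The number matters because the candidates are different sets of people. The 139 appears to be a count of those who had not discontinued. A dataset or flow diagram built on it would leave out every provider who had discontinued by then, under an intention-to-treat label. The 151 would leave out 38 providers by an unknown criterion. In either case the missing-data percentages in 5.5, which are calculated on 189, would no longer describe the analysed population.

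**Working it through.** **1. What 139 is.** Site rows in Protocol 10.0:

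- Consented: 17+19+18+29+18+16+11+15+24+23 = 190.
- Discontinued: 6+6+8+9+3+4+1+4+5+5 = 51.
- Active: 11+13+10+20+15+12+10+11+19+18 = 139.

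Consented minus discontinued equals active at all ten sites, and 190 − 51 = 139. Under Protocol 2.0 and 22.0, completing a role play is consent, so the 51 had also taken part.

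**2. Which count fits the power inputs.** Sites × mean providers per site: 10 × 18.9 = 189. Observations ÷ providers, against the stated average of 6.5:

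| Providers | 1,237 ÷ providers |
|---|---|
| 189 | 6.54 |
| 151 | 8.19 |
| 139 | 8.90 |

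**3. The SAP's effective sample sizes, reproduced.** I read the design-effect formula as n_eff = n / (1 + (m − 1)ρ), where m is the cluster size.

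- Within providers: m = 1,237/189 = 6.545 and ρ = 0.35, so 1,237 / (1 + 5.545 × 0.35) = 420.6 (stated 420).
- Within sites: m = 420/10 = 42 and ρ = 0.09, so 420 / (1 + 41 × 0.09) = 89.6 (stated 90).

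The SAP's chain is therefore built on 189 providers.

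**4. Which count fits the missing-data percentages.**

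- 75% of 189 = 141.8. Allowing for rounding (74.5% to 75.5%), 141 or 142 providers had implementation data, which is already more than 139.
- 99% of 189 = 187.1, so about 187 providers had baseline data, which is more than 151.
- 49% of 189 = 92.6. None of the three products (187, 142, 93) gives 151 or 139.

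**5. Effect on power.** The chain in step 3 was repeated for each count in two ways: at 6.5 measurements per provider, and with the 1,237 observations held fixed. Power is for R² = 0.09. I assume one predictor and two-sided 0.05, because the SAP states neither the sidedness nor a target power.

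| Providers | n_eff at 6.5 each | Power | n_eff, 1,237 fixed | Power |
|---|---|---|---|---|
| 189 | 89.6 | 0.84 | 89.6 | 0.84 |
| 151 | 85.4 | 0.82 | 86.3 | 0.82 |
| 139 | 83.7 | 0.81 | 85.0 | 0.82 |

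For 151, for example: 151 × 6.5 = 981.5; 981.5 / 2.925 = 335.6; 335.6 / (1 + 32.56 × 0.09) = 85.4.

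**6. Who would be left out.** Using 139: 51/190 = 27% of those consented. Using 151: (189 − 151)/189 = 38/189 = 20%.

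**The case against.** The strongest reply is that every passage that governs the analysis already points to the full set. SAP 3.3.1 and 5.5 both use 189. SAP 5.5 plans maximum likelihood on all available data (if no non-random missingness is found), together with a pattern-mixture check. Protocol 14.0 keeps leavers' data. Nothing says that the primary model will be restricted to 139 or 151. The sentence in 3.1 still holds an unfilled patient count, so its 139 may simply be an uncorrected carry-over. This stands, and it rules out several stronger readings that a reader might infer:

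- **That the plan will analyse survivors.** No analysis text says so. The selection problem is conditional on someone using the wrong count.
- **That 5.1.5 promises to keep every provider and so implies 189.** Its wording governs how a provider is classified by site, cluster and phase. It does not say who is included.
- **That the 51 left after their site was randomised.** Sites were randomised in waves (SAP 3.2), while assessments began for all sites in the first baseline month (SAP 3.7). The protocol table gives no discontinuation dates, so some may have left before their site's draw.
- **That 151 is simply an error.** Protocol 5.0 lets participants continue past baseline only if they attended at least half of the workshop. That rule would create a subset, but neither document counts who met it, so it can be neither tied to 151 nor excluded.

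The reply does not remove the contradiction. All three counts stand in current SAP text, and 3.3 calls 151 final.

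**Conclusion.** The point holds as an inconsistency in the stated sample size combined with an undefined analysis population. It does not show a biased analysis. Of the SAP's three counts, 189 is the only one compatible with its own observations, effective sample sizes and missing-data percentages. That 139 was taken from the protocol's table is an inference, since the SAP does not cite a source, but the exact match and the protocol's current-N label make it a strong one. The origin of 151, and the difference of one between 189 and 190, cannot be settled from the documents.

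The consequence for power is minor: about 0.84 against 0.81 to 0.82, on the assumptions in the working. The possible consequence for who is analysed is larger, at 20% or 27% left out, but it arises only if the dataset or flow diagram follows 3.3 or 3.1. Confidence is high for the inconsistency. The plan should be corrected because the error is clear and the repair is cheap.

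**What to change.** 1. Reconcile 190, 189, 151 and 139 against the enrolment log, and show the result in the participant flow.
2. Make SAP 3.1 and 3.3 state the same all-enrolled number that 3.3.1 and 5.5 use: 189, unless the log shows otherwise.
3. Explain 189 against 190. A request for data deletion is one possibility, but the documents do not say so.
4. Label 139, wherever it is kept, as the number active at the start of cycle 8.
5. Either give the rule behind 151 and name it as a subset, or delete it.
6. State in SAP 5.1.5 that the primary set is every enrolled provider with at least one MI-CRS role play, including those who discontinued, unless they asked for their data to be removed.

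The cost is SAP wording and one check of the enrolment log. No new data are needed.

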3.3.1. Primary Objective

For Aim 1 (i.e., the effect of TMI on provider MI competence), estimation of power for mixed-effects regression models is complex because of the number of parameters involved, and in the present case, this is further complicated by the DWLD. Traditionally, and for conventional mixed-effects power analysis software, intervention condition is modeled at the highest level, and the intervention effect is the cross-level interaction between condition and a level-1 growth term. In the present case, because each provider has measurements in each of three research phases—that is, the intervention condition changes over time for each provider—the terms for testing the intervention effect are modeled at level-1 (i.e., time and phase terms). As such, a special method was required to estimate power, which was based on Hox (2018). There were three steps: (1) Compute the *actual* sample size of observations. For the primary outcome of provider MI competence, with 10 sites, an average of 18.9 providers each, and an average of 6.5 measurements per provider, there were 1,237 observations (i.e., non-independent, nested observations). (2) Penalize the sample of observations for nesting effects using a reorganization of the design effect formula (i.e., $neff = n / \{1+nclus - 1\} \rho$), the result of which is the *effective* sample size: the sample size of truly independent observations after adjusting the observed sample size for nesting effects that decrease statistical power. This step was performed twice, first to adjust for repeated measurements within providers and then to adjust for providers within sites. The supplied values for ρ were based on estimates from a fully unconditional, three-level mixed-effects regression model for the MI competence outcome. Note that the final models will not estimate a random effect for sites (due to the small number), and instead, they will control site effects using fixed effect indicators. For the purpose of power analysis, the site penalty was applied to provide a more conservative estimate. For the provider MI competence outcome, with a nesting effect of $\rho = .35$ for repeated measurements within providers, the sample of 1,237 non-independent observations provides the statistical power of 420 independent observations. The sample of 420 observations, with a nesting effect of $\rho = .09$ for providers in sites, provides statistical power equivalent to 90 truly independent observations. (3) Power was then estimated for a conventional, single-level regression model with the effective sample size of independent observations, which indicated that the effective sample of 90 independent observations was sufficient to detect a small-to-medium effect of $R^2 = .09$. Thus, power is sufficient to detect the effects of interest, though it is important to note that, due to the specific features of the design, this method did not directly account for the number of parameters in the model or the reliability of estimated slopes.

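### The 90 effective observations in SAP 3.3.1 come from design effects for predictors that are constant within provider and site, so the stated power is not that of the phase contrast in SAP 5.4.1

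*SAP*

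**What the plan says.** SAP 3.3.1 explains that conventional power software does not fit this design. It puts the time and phase terms at level 1 "because each provider has measurements in each of three research phases". It then works in three steps.

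- **Observations:** "with 10 sites, an average of 18.9 providers each, and an average of 6.5 measurements per provider, there were 1,237 observations".
- **Penalties:** with ρ = .35 "for repeated measurements within providers, the sample of 1,237 non-independent observations provides the statistical power of 420 independent observations"; those 420, with ρ = .09 "for providers in sites, provides statistical power equivalent to 90 truly independent observations". The ρ values "were based on estimates from a fully unconditional, three-level mixed-effects regression model for the MI competence outcome".
- **Power:** "Power was then estimated for a conventional, single-level regression model with the effective sample size of independent observations", with the result that "the effective sample of 90 independent observations was sufficient to detect a small-to-medium effect of" R² = .09.

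The section makes two disclosures. The site penalty is deliberately conservative, because the final models use fixed site indicators. The method also does not directly cover the number of parameters or the reliability of slopes. It gives no target power, no number of tested predictors and no effect in MI-CRS points.

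SAP 5.4.1 describes the primary analysis as a two-level mixed model with phase indicators, time terms, and cluster or site fixed effects. SAP 5.5 reports that, of 189 providers, "75% had at least one measurement during the implementation phase, and 49% had at least one measurement during the sustainment phase".

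**The concern.** The factor 1+(m−1)ρ is the variance inflation of a cluster mean, or of the coefficient of a predictor that takes one value throughout the cluster. A phase indicator is neither. Each provider who stays in the study passes from baseline to implementation, and so does each site. Stable differences between providers and between sites therefore largely cancel from the contrast.

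What costs precision is different. Phase advances with calendar time, so its effect must be separated from a time trend, and sites may differ in their time course or in their response to TMI. The calculation contains neither. Its ρ values come from a model without phase or time terms, so they carry no information on these components.

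At stake is how a null or borderline result is read. Someone who relies on R² = .09 as the detectable effect would be using the sensitivity of a different test. They would also apply one figure to implementation and sustainment, whose precision must differ given 75% and 49% coverage.

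**Working it through.** **1. Reproduce the SAP.** Inputs from SAP 3.3.1: 1,237 observations, 10 sites, 18.9 providers per site (189, as in SAP 5.5), ρ = .35 and .09.

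- Measurements per provider: 1,237/189 = 6.545. First penalty: 1 + 5.545 × .35 = 2.94; 1,237/2.94 = 420.6.
- Effective observations per site: 420/10 = 42. Second penalty: 1 + 41 × .09 = 4.69; 420/4.69 = 89.6. (Using 18.9 providers as cluster size gives 420/2.611 = 161, so the SAP used 42.)

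Both stated figures are confirmed.

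**2. Power at N = 90.** f² = .09/.91 = .099; noncentrality 90 × .099 = 8.9; F test on 1 and 88 df at two-sided alpha .05 (sidedness assumed). Power = .839.

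**3. Does the factor fit?** For a contrast purely within provider and without time terms, the variance factor is about 1 − ρ = .65, against the 2.94 applied. Substituting .65 is not the remedy: 1,237/.65 = 1,903 would overstate precision, because phase is assigned by site in waves and moves with study time.

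**4. Cost of the time overlap.** In one reconstruction, implementation covers .377 of observations. The residual variance is 1 − .35 − .09 = .56, and the variance inflation from linear time, the sustainment indicator and cluster indicators is 3.04. Then SE = √[.56 × 3.04 / (1,237 × .377 × .623)] = √(1.702/290.5) = .077, and 2.8 × SE is about .21 SD at 80% power. The phase share and the inflation factor are reconstructed, not given.

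**5. Implementation, over a range of assumptions.** This uses generalized least squares on a reconstructed schedule:

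- 10 sites and 13 occasions, with 2/3/4/5/6 baseline occasions by cluster (Protocol 6.0 gives 2 to 6), four in implementation and the rest in sustainment;
- 75% and 49% retention; 1,289 simulated observations against 1,237;
- provider variance .35, residual .65, site fixed effects.

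Detectable shift at 80% power, in SD:

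| Terms | No added heterogeneity | Site-by-period .05 | Site-by-period .09, site-by-TMI .09, provider-by-TMI .10 |
|---|---|---|---|
| Phase only | .16 | .22 | .38 |
| + linear time | .25 | .33 | .47 |
| + phase slopes | .30 | .40 | .55 |

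Expressed as n = 4/SE² for a balanced contrast, these run from about 1,215 down to 105.

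Figure implied by the SAP: for a balanced contrast with N = 90, SE = 2/√90 = .211, and 2.80 × .211 = .59 SD. Alternatively, if all of R² = .09 belongs to one indicator covering a share p, the shift is .30/√[p(1−p)]: .60 at p = .50 and .62 at p = .377. That is roughly .6 SD.

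**6. Sustainment.** All of these have study time in the model.

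- Provider variance .35 and residual .56: .40 SD (common slope) to .52 SD (phase slopes).
- Adding site-by-TMI variance .09: .48 to .61 SD.
- Heavier combined heterogeneity: up to about .89 SD.
- Implied by the SAP: .30/√(.30 × .70) = .65 at a 30% share, and .30/√(.155 × .845) = .83 at a 15.5% share. No document gives the share.

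**7. Coverage by phase.** .75 × 189 = 142 providers with any implementation measurement and .49 × 189 = 93 with any sustainment measurement. The statement that every provider is measured in all three phases cannot stand beside SAP 5.5.

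**The case against.** The SAP presents this as a special method, states openly that the site penalty errs on the safe side, and names two things it leaves out. The calculation is retrospective: it uses observed counts and estimated ρ values, and the Protocol says enrolment is closed. For implementation, every scenario above supports the SAP's conclusion with room to spare. Hypotheses 2 and 3, on sustainment, are labelled exploratory in SAP 2.2.1. SAP 5.1.1 promises 95% confidence intervals for all effects, and those are the better guide to a null result. The sentence on three phases explains why the terms sit at level 1; it does not feed the inputs, since 6.5 of a possible 13 measurements already reflects missed occasions.

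All of that stands, and it limits the consequence. It does not make the figure right. The disclosures cover the site penalty, parameter count and slope reliability. They do not say that the provider penalty fails to fit a level-1 term, or that phase overlaps with time.

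Two stronger readings should be set aside. A reader might infer that power at N = 90 falls short because several parameters are tested jointly; SAP 5.1.1 specifies Wald tests of coefficient over standard error, which have 1 df. A reader might also dispute the small-to-medium label by converting R² to an SD shift; the label describes R² in its own metric, and the conversion needs a phase share that the documents do not give.

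**Conclusion.** The point holds as one of method, of minor to moderate weight. The arithmetic of SAP 3.3.1 is correct, but 90 effective observations and R² = .09 describe a single-level test with penalties suited to cluster-constant predictors, not the phase contrast of SAP 5.4.1.

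For implementation the figure is probably conservative, by an amount the documents cannot fix. For sustainment, conservatism is not assured, because the detectable and implied ranges overlap. Both statements rest on an assumed schedule and on assumed site-by-period, site-by-TMI and provider-by-TMI variances.

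A reader might infer that the trial is underpowered. The documents do not support that: in every scenario tried for implementation the design detects a smaller shift than the SAP's figure implies, although still stronger site heterogeneity could remove the margin. Nor do they support a fixed multiple by which the stated effect is too large: across the table in the working, the ratio to .59 SD runs from .59/.55 = 1.1 to .59/.16 = 3.7.

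**What to change.** - Replace steps 2 and 3 of SAP 3.3.1 with the standard error of the Hypothesis 1 phase contrast from the actual design matrix: observed occasions and phases, a provider random effect, study time, cluster or site terms, and a stated range for site-by-period and site-by-treatment variance.
- State the detectable shift in MI-CRS points, with the power level, alpha and sidedness, separately for implementation and sustainment.
- Correct the statement on measurements in all three phases so that it agrees with the 75% and 49% in SAP 5.5.

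The sponsor already holds the observed measurement pattern, so the cost is one calculation and a rewritten paragraph. Enrolment, assessments and the primary model do not change.
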